5.5.4.3.2 Reporting of serious adverse events

All SAEs occurring after study drug initiation and up to the end of study visit (Visit 9, Week 10) must be reported on AE pages in the CRF and on an SAE form, regardless of the investigator-attributed causal relationship with study treatment.

Abnormal laboratory findings

Abnormal laboratory findings, if serious, must be reported on specific AE pages of the CRF.

Following laboratory variables are collected for the assessment of efficacy (see Section 6.5.3.2) at screening and during the treatment period, and are not required to be reported as SAEs as described above: WBC including differential counts, RBC, Hgb, platelet count, fibrinogen, complement C3/C4, PT-INR, and cardiac troponin; ALT, AST, total bilirubin, creatinine, ferritin, LDH, D-dimer, CRP, electrolytes (sodium, potassium, calcium), and glucose.

5.5.4.3.3 Follow-up of serious adverse events

Serious adverse events still ongoing at the end of study visit (Visit 9, Week 10) must be followed up until resolution or stabilization, or until a definite event outcome is provided, e.g., resolved with sequelae or death.

5.5.4.3.4 Reporting procedures

All SAEs must be reported by the investigator to the Sobi drug safety department within 24 hours of the investigator's first knowledge of the event.

All SAEs must be recorded on an SAE form, irrespective of the study treatment received by the patient, and whether or not this event is considered by the investigator to be related to study treatment.

The SAE forms must be e-mailed to the Sobi drug safety department:

• [contact]

The investigator must complete the SAE form in English, and must assess the causal relationship of the event to study treatment.

Follow-up information about a previously reported SAE must also be reported within 24 hours of receiving it. The Sobi drug safety department may contact the investigator to obtain further information.

If the patient is hospitalized in a hospital other than the study site, it is the investigator's responsibility to contact this hospital to obtain all SAE relevant information and documentation.

The reference safety document to assess expectedness of a suspected serious adverse reaction and for reporting by the Sponsor to Health Authorities, IRBs/IECs, and investigators is:

- For emapalumab the reference safety information section of the Investigator's Brochure [Emapalumab IB].
- For anakinra Section 4.8. of anakinra SmPC (Kineret SmPC) + i.v. data

5.5.4.4 Pregnancy

5.5.4.4.1 Reporting of pregnancy

Irrespective of the treatment received by the patient, any pregnancy occurring after study drug initiation up to the end of study visit (Visit 9, Week 10) must be reported within 24 hours of the investigator's knowledge of the event. Pregnancies of female patients will be followed until final outcome of pregnancy. For emapalumab treated patients; Pregnancies of a female partner of male patients in the study need to be similarly reported and to be followed until the final outcome of the pregnancy

Pregnancies must be reported on the pregnancy form which is e-mailed to the Sobi drug safety department ([contact]), and on an AE page in the CRF.

5.5.4.4.2 Follow-up of pregnancy

Any pregnancy must be followed to its conclusion and its outcome must be reported to the Sobi drug safety department. This information will be only entered in the drug safety database.

Sobi	
Emapalumab/Anakinra	Clinical Study No: Sobi.IMMUNO-101

Any AE associated with the pregnancy occurring during the study must be reported on separate AE pages in the CRF. Any SAE occurring during the pregnancy must be reported on an SAE form as described in Section 5.5.4.3.

5.5.4.5 Laboratory safety assessments

For details on laboratory assessments, see Section 5.5.3.7.

5.5.4.6 Vital signs

Vital signs (body temperature, blood pressure, heart rate. respiratory rate and oxygen saturation) will be measured at screening, and Visit 1 to 7, and recorded in the CRF.

For AE reporting of abnormalities, see Section 5.5.4.3.

5.5.4.7 Electrocardiograms

A 12-lead ECG recording will be performed at screening, Visit 6 (Day 15) and Visit 7 (Day 28), and recorded in the CRF. The ECG assessments will be performed at site and will be reported as "normal" or "abnormal". Any abnormalities should be specified. Abnormalities reported at screening should be recorded as medical history.

For AE reporting of abnormalities, see Section 5.5.4.3.

5.5.4.8 Pregnancy Test

Female of childbearing potential will have a urine pregnancy test taken at screening and at Visit 6 (Day 15). The outcome of the test will be reported as "positive" or "negative" in the CRF.

5.5.4.9 Immunogenicity

Immunogenicity samples will be collected for all patients receiving active study treatment at Visit 1 Pre-dose, at Visit 6 at end-of infusion (for anakinra a sample should be taken after the first infusion per day) at Visit 7. If the patient is coming to the clinic at the follow-up visits, immunogenicity samples will also be collected at Visit 8 and Visit 9. The date and time of blood sampling will be recorded in the CRF. Samples will be sent to central laboratory for analysis.

5.5.4.10 Viral shedding

Samples for viral shedding will be collected for all patients at Visits 1, 4, 6 (Day 15) and 7 (Day 28). For patients coming to the clinic for the follow-up visit, samples will also be collected at Visit 8 and Visit 9. The date of the sampling will be recorded in the CRF. Samples will be sent to a central laboratory for analysis.

5.5.4.11 Data Review Committee

The Data Review Committee members are to be independent from any of the sponsors and without any conflicts of interest, providing their expertise in intensive care, inflammation, infectious diseases and will be involved in study oversight, safety monitoring and interpretation of the emerging study results.

5.5.4.12 Safety Review Committee

An SRC consisting of internal Sobi members (voting) and coordinating investigators (nonvoting) members is established to monitor study participant safety in the study. Clinical study safety information (eg AEs, SAEs, laboratory values, ECGs, vital signs, and additional safety related study assessments, as required) is monitored and reviewed on a continuous basis by SRC from study start to database lock.

If two patients develops a life threatening or fatal adverse event suspected to be study drug related then an ad hoc SRC meeting will be held within 24 hours after the Sponsor awareness of the Event. At this meeting the decision on continuation of the study with or without changes or to halt the enrollment of the specific study arm will be taken. Details are described in a separate written operating procedures for the SRC.

5.5.4.13 Specific safety monitoring and management during the study

Infusion related reactions for all treatment arms:

The infusion related reactions will be closely monitored by the treating physician. Should severe allergic reactions (such as anaphylactic shock) occur, the patient would be managed according to the local standard treatment guidelines.

Anakinra treatment:

• Neutrophil counts should be assessed prior to initiating and during anakinra treatment. Should neutropenia (neutrophil count < $1.0 \times 10^{9}/L$) occur in a patient treated with anakinra, dose reduction or discontinuation of the treatment may be considered as judged by the investigator. Should neutropenia (neutrophil count < $0.5 \times 10^{9}/L$) occur in a patient treated with anakinra, the treatment should be discontinued.

• Anakinra is mainly eliminated by the kidney. Should severe renal impairment (CLcr < 30 ml/min) or end stage renal disease occur, the reduction of anakinra dose (100mg IV 2 times daily) should be considered as judged by the investigator.

Emapalumab treatment:

Monitoring of new infections is requested throughout the study. Type of investigation, specimen, result and pathogen identified will be captured in the CRF. Such data will be captured for all new infection. Should serious infection caused by pathogens potentially favored by IFNγ neutralization, i.e. mycobacteria, histoplasma capsulatum, herpes zoster, salmonella and shigella occur in a patient treated with emapalumab, the treatment should be stopped, and appropriate anti-infective treatment should be initiated.

5.5.5 Exploratory assessments

5.5.5.1 Clinical Status

Data on clinical status based on a 7-point ordinal scale will be collected at Visits 1 to 9 and recorded in the CRF.

The scale consists of the following categories:

- 1. Death
- 2. Hospitalized, requiring invasive mechanical ventilation or extracorporeal membrane oxygenation (ECMO)
- 3. Hospitalized, requiring non-invasive ventilation or high flow oxygen devices
- 4. Hospitalized, requiring supplemental oxygen
- 5. Hospitalized, not requiring supplemental oxygen requiring ongoing medical care
- 6. Hospitalized, not requiring supplemental oxygen no longer requires ongoing medical care
- 7. Not hospitalized

5.5.5.2 Pharmacokinetics

PK blood samples will be collected for all patients receiving active study treatment. At Visit 1 sampling should be done pre-dose and at end-of infusion and during Visits 2, 3, 4, 5 and 6 a PK sample should be taken at end-of infusion. For anakinra treated patients; samples will only be collected in connection with the first infusion per day. In addition, for emapalumab treated patients, a PK sample will be collected also at Visit 7 (Day 28) and during follow-up on Visit 8 and 9 in case the patient is at the clinic for these visits. It should be noted that a separate iv line will have to be used when collecting the PK samples, ie not the same iv line as used for the iv infusion of active study treatment.

The date and time of blood sampling will be recorded in the CRF. Samples will be sent to a central laboratory for analysis.

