4.3.1 Exploratory endpoints

Clinical status based on a 7-point ordinal scale.

The scale consists of the the following categories:

- 1. Death
- 2. Hospitalized, requiring invasive mechanical ventilation or extracorporeal membrane oxygenation (ECMO)
- 3. Hospitalized, requiring non-invasive ventilation or high flow oxygen devices
- 4. Hospitalized, requiring supplemental oxygen
- 5. Hospitalized, not requiring supplemental oxygen requiring ongoing medical care
- 6. Hospitalized, not requiring supplemental oxygen no longer requires ongoing medical care
- 7. Not hospitalized

PK parameters will be calculated for emapalumab and anakinra by non-compartmental analysis and population analysis, as applicable.

PD biomarkers: Change from baseline in CXCL9, IFN γ , IL-1, IL-6, sIL-2R and selected biomarkers relevant for hyperinflammation.

5 Investigational plan

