5.4.5 Selection and timing of doses for each patient

5.4.5.1 Emapalumab

Emapalumab will be administered by intravenous (i.v.) infusion over a period of 1 to 2 hours depending on the volume to be infused, at an initial dose of 6 mg/kg.

Emapalumab treatment will be continued at the dose of 3 mg/kg, every 3rd day until Day 13 i.e., Days 4, 7, 10 and 13. The following information will be recorded in the CRF for each emapalumab administration: date, start and end time, total dose infused, and, if infusion was interrupted, reason for interruption.

Emapalumab must be prepared by a Pharmacist or other appropriately qualified staff member, specifically authorized by the Investigator/Pharmacist and appropriately licensed to perform the task.

The specific dose to be administered for an individual infusion will be determined based on the patient's body weight at screening.

Full instructions for the preparation of emapalumab, including dilution steps and method for administration, are available in the IMP manual.

The patient should receive the designated volume of the infusion material through an infusion pump over 1 to 2 hours depending on the volume to infuse. A 0.2 μ m filter must be included in all infusion lines.

It is recommended that an i.v. central line remains in place to ensure venous access during the treatment period.

Since no data are available on the compatibility of emapalumab with other i.v. substances or additives, other medications/substances should not be added to the infusion material or infused simultaneously through the same i.v. line. If the same i.v. line is used for subsequent infusions of other drugs, the line should be flushed appropriately with saline before and after infusion of emapalumab.

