### **12.4.2 Pharmacokinetics**

PK data will be listed and summarized at each visit with descriptive statistics.

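### Anakinra PK is sampled after dosing only at end of infusion, so non-compartmental analysis cannot give AUC, half-life or clearance; the Visit 6 antibody timing also needs revising for anakinra and reconciling for emapalumab

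*Protocol*

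**What the plan says.** **PK sampling.** Protocol 5.5.5.2 takes a sample before the dose and one at end of infusion at Visit 1. After that, "during Visits 2, 3, 4, 5 and 6 a PK sample should be taken at end-of infusion". For one arm there is a restriction: "For anakinra treated patients; samples will only be collected in connection with the first infusion per day". Section 5.5.5.2 extends sampling to Visit 7, and to Visits 8 and 9 if the patient attends, for emapalumab patients only.

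**PK endpoint.** Protocol 4.3.1 and SAP 3.4.4 both state: "PK parameters will be calculated for emapalumab and anakinra by non-compartmental analysis and population analysis, as applicable". Neither names a parameter. SAP 12.4.2 plans less: "PK data will be listed and summarized at each visit with descriptive statistics".

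**Antibody sampling.** Protocol 5.5.4.9 takes samples before the dose at Visit 1, then "at Visit 6 at end-of infusion (for anakinra a sample should be taken after the first infusion per day"), then at Visit 7 (Day 28), and at Visits 8 and 9 if the patient comes to the clinic. Presence of anti-drug antibodies is a secondary safety endpoint (Protocol 4.2.1). Protocol 7.3.4.2 summarises it at each assessment.

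**Dosing.** Anakinra is infused over 60 minutes every 6 hours on Days 1 to 15 (Protocol 5.4.5.2). Emapalumab maintenance runs "every 3rd day until Day 13 i.e., Days 4, 7, 10 and 13" (Protocol 5.4.5.1). Visit 6 is Day 15, with a window of one day either side.

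**The concern.** Non-compartmental analysis obtains a terminal slope, and hence half-life, AUC and clearance, from concentrations measured while drug is falling. The anakinra schedule in 5.5.5.2 contains none. Clearance is of real interest here: Protocol 5.5.4.13 notes that anakinra is mainly eliminated by the kidney.

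The antibody sample raises a related question. Circulating drug can interfere with an antibody assay, and the only on-treatment anakinra sample comes straight after an infusion. If the assay tolerates drug poorly, the Visit 6 positivity rate could read too low.

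For emapalumab the problem is one of consistency: Visit 6 PK and antibody samples are timed to an infusion that is not on the schedule. The exemption letter in Appendix 3 says that no sample handling procedure will be provided, so where that applies a site has little beyond this text to go on.

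**Working it through.** The plan gives no figure to reproduce. The check is a count of samples plus a simple model.

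**1. Count, anakinra, per patient (5.5.5.2).** Pre-dose: 1 (Visit 1, no drug yet). End of infusion: 6 (Visits 1 to 6). Trough: 0. Declining phase: 0. Post-treatment: 0. With 18 patients in the arm, that is up to 18 × 6 = 108 post-dose concentrations, all at one point of the dosing cycle.

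**2. What those samples can show.** Assume one compartment, a 1-hour infusion and a 6-hour interval (5.4.5.2). The documents give no half-life, so it is varied as an assumption, with k = ln 2 / half-life.

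- Accumulation of end-of-infusion levels, steady state over first dose: 1 / (1 − exp(−6k))
- Trough over end-of-infusion level: exp(−5k)
- Share of the steady-state interval AUC lying after end of infusion: (1 − exp(−k))(1 − exp(−5k)) / [k(1 − exp(−6k))]

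| Assumed half-life (h) | Accumulation | Trough / end of infusion | AUC share after end of infusion |
|---|---|---|---|
| 1 | 1.02 | 0.031 | 0.71 |
| 2 | 1.14 | 0.177 | 0.80 |
| 3 | 1.33 | 0.315 | 0.82 |
| 4 | 1.55 | 0.420 | 0.82 |
| 6 | 2.00 | 0.561 | 0.83 |
| 12 | 3.41 | 0.749 | 0.83 |

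Most of the exposure is unobserved, and the unmeasured trough could be anywhere from 3% to 75% of the measured level. The only information on elimination is the accumulation ratio, which is close to 1 when the half-life is short.

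**3. Anakinra antibodies.** Visit 6 is drawn after an infusion, near peak. Visit 7 is Day 28 ± 3, so 10 to 16 days after the last anakinra day (Day 15). At the earliest, 240 hours, a 12-hour half-life leaves 2^(−20), about 1e-6 of the level. The Day 28 sample is effectively free of anakinra.

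A pre-infusion sample at Visit 6 would face less drug by a factor of 1/0.561 = 1.8 (6-hour half-life) to 1/0.177 = 5.7 (2-hour half-life).

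**4. Emapalumab at Visit 6.** Infusions fall on Days 1, 4, 7, 10 and 13. Visit 6 is Day 15, or Day 14 to 16 with its window. No emapalumab infusion falls in that range, yet 5.5.4.9, 5.5.5.2 and Table 2 footnotes 15 and 16 time the samples to the end of one.

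**5. Visits 8 and 9.** Section 5.5.5.2 limits later PK samples to emapalumab. Footnote 15 limits Visit 7 that way, but its sentence on Visits 8 and 9 carries no such limit, and the Table 2 row is labelled for both drugs.

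**The case against.** **A reader might infer that the anakinra PK endpoint fails altogether.** The documents do not support that. The endpoint adds population analysis and the qualifier as applicable, and promises no specific parameter. SAP 12.4.2 plans only listings and summaries by visit, which the schedule fully supports. An end-of-infusion concentration and an accumulation ratio can be derived.

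Nor is the population route empty. As an illustration, assume 18 complete patients, each with one first-dose and five later end-of-infusion levels, and log-normal within-patient variation with SD s = √ln(1 + CV²). The standard error of the mean log ratio is s × √(1 + 1/5) / √18. At 30% CV that is 0.294 × 1.095 / 4.243 = 0.076, so a ratio of 1.33 (3 hours) lies about 3.8 standard errors from 1, and 1.14 (2 hours) about 1.8. At 50% CV they lie about 2.4 and 1.1. A group-level signal is therefore plausible except at short half-lives. This objection stands. What survives it is that individual estimates would be weak, and that AUC, half-life and clearance remain out of reach of non-compartmental analysis.

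**A reader might infer that antibody results are biased toward negative.** That depends on an assay drug tolerance the documents do not give, and the Day 28 sample is scheduled for every actively treated patient and is effectively free of anakinra. This largely stands. The remaining gap is the Visit 6 rate itself, antibodies present only during treatment, and patients who die or withdraw before Day 28. Protocol 5.4.7.2 withdraws patients given the listed rescue agents, and 5.3.3.2 steers their last assessments to the Visit 6 schedule.

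**A reader might extend the near-peak argument to both arms.** It does not apply to emapalumab, which has no infusion at Visit 6.

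**Conclusion.** The point holds in limited form. For anakinra, the stated non-compartmental analysis cannot give AUC, half-life or clearance from the 5.5.5.2 schedule. This follows from the sampling times alone and needs no assumed half-life. A population model would be weakly informed about elimination, most of all if the half-life is short; that part rests on the one-compartment model and the assumed range.

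Understated anakinra antibody positivity at Visit 6 is a possibility, not a finding, because assay tolerance is unknown. The emapalumab Visit 6 timing is a plain inconsistency and must be reconciled.

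The stakes are modest: PK is exploratory, immunogenicity is one of several safety endpoints, and neither the primary endpoint nor any stopping rule is touched. It is worth correcting because the correction is cheap.

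**What to change.** Keep the number of draws and move some of them.

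- **Anakinra PK:** at two of Visits 2 to 5 (for example Visits 3 and 5), draw immediately before the first infusion of the day.
- **Visit 6:** draw the anakinra PK and antibody samples before the first infusion. Define the emapalumab samples as taken at the visit, with no infusion reference.
- **Alignment:** make 5.5.4.9, 5.5.5.2 and Table 2 footnotes 15 and 16 agree, and state whether anakinra patients give PK samples at Visits 8 and 9.
- **Endpoint wording:** limit non-compartmental analysis for anakinra to the parameters the schedule supports. Even after the change, peaks and troughs come from different days and serve a population model better than a full profile.
- **Assay:** state the drug tolerance.

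An anakinra patient would then give three end-of-infusion levels (Visit 1 and two of Visits 2 to 5) and three troughs, instead of six and none. Infusion start and end times and draw times are already recorded in the CRF (5.4.5.2, 5.5.5.2), so the troughs can be interpreted. The change also follows the preference in 5.5.1.3 to 5.5.1.5 for assessments before IMP.

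The cost is protocol wording, fewer peak concentrations, and loss of pairing with the end-of-infusion PD sample (5.5.5.3) at the moved visits. A pre-infusion Visit 6 sample reduces drug interference but does not remove it.

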5.5.5.3 Pharmacodynamics

Blood samples for determination of CXCL9, IFN γ , IL-1, IL-6, sIL-2R and selected exploratory parameters will be collected at Visit 1 to 9 at the end of infusion (for anakinra treated patients; samples will only be collected in connection with the first infusion per day). The date and time of blood sampling will be recorded in the CRF. It should be noted that a separate iv line will have to be used when collecting the PD samples, ie not the same iv line as used for the iv infusion of active study treatment.

Samples will be sent to a central laboratory for analysis.

6 Quality control and quality assurance

This study will be conducted in compliance with this protocol, study specific procedures, CRO SOPs, Sobi SOPs, the ICH Guideline for GCP [1], and applicable regulatory requirements.

Version 7.0 Final Protocol, Date 24 Jun 2020

The Sponsor/CRO will establish a systematic, prioritized, risk-based approach to monitoring and, considering the current situation, will need to utilize remote monitoring. The Sponsor/CRO will develop a risk management plan with the aim to limit the contacts with patients and site personnel during the emergency period, while ensuring the patients safety and integrity, compliance with the protocol, study specific procedures and applicable regulatory requirements.

To ensure ongoing patient safety and well-being, and control risks to study critical processes, such as review of all informed consent forms and all primary efficacy variables, alternative mechanisms of oversight will be introduced (such as phone calls, video calls, remote monitoring etc). The Sponsor/CRO will also investigate if other measures for sharing data can be implemented, e.g. sharing de-identified source documents in shared drives/locations.

On-site monitoring visits will be postponed until the emergency period is over. Source documents will then be reviewed for verification of agreement with data in CRFs.

The investigator or institution guarantees access to source documents by Sobi, its representatives, and appropriate regulatory agencies.

The study site may be subject to a quality assurance audit by Sobi or its representatives, as well as inspection by appropriate regulatory agencies.

It is important that the investigator(s) and the(ir) relevant personnel are available during the monitoring visits and possible audits and that sufficient time is devoted to the process.

7 Statistical plan

